Improvements in cardiorespiratory fitness in response to exercise training varies greatly between individuals, with some people responding well or very well ('responders' or 'high-responders') to exercise training, whereas others only have mild increases in their cardiorespiratory fitness following similar exercise training ('low-responders') [2-4, 23, 24]. The ability to change cardiorespiratory fitness is a multifactorial trait [2, 4]. Considering cardiorespiratory fitness is one of the best integrative predictors of morbidity and mortality risk, it is important to understand how factors, such as genetics and environmental influences (e.g. training and diet), may predict the variability in response to exercise training. This knowledge could lead to targeted personalised exercise therapy to decrease the burden of chronic disease.

Predictor genes for $\dot{V}O_{2\max}$ trainability

From our systematic review, 35 studies identified 97 genes that predict $\dot{V}O_{2\max}$ trainability [6]. Exercise-related phenotypes are complex traits and are polygenic (i.e. influenced by many genes working together) with each genetic variant likely to be contributing a small percentage (typically less than 1%) to the overall change in $\dot{V}O_{2\max}$.

Approximately, 50% of the variance in $\dot{V}O_{2\max}$ trainability can be attributed to genetic make-up. A gene predictor score (GPS) based on these variants can predict who may be a lower or higher responder to training. A score of '0' represents homozygote (two copies of the same allele) for the low-response variant; '1' represents heterozygous (two different alleles, with one a high response allele) and '2' represents homozygous for the high-response allele. Individuals with a low score (e.g. <9 high response alleles) may be a lower responder to training.

Possible Gene Expression Mediators

Training intervention

HIIT has a lower frequency of 'non-responders' [7]; and greater improvements in vascular function, cardiorespiratory fitness and other biomarkers compared to other forms of training [7, 25]. This training requires individuals to exercise at a high intensity (e.g. 90% of maximum heart rate) for a specific period of time (e.g. 4 minutes) with a rest/recovery period (e.g. 3 minutes) in between [26].

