Our gut microbiome is predetermined by host genetics that can be manipulated through numerous external factors, such as exercise and diet. Whilst host genetics and associated gut taxa increases susceptibility to various chronic diseases and overall fitness levels, the relationship between the gut microbiome and $\dot{V}O_{2max}$ trainability is unknown.

In addition to examining the gene predictor score for $\dot{V}O_{2max}$ trainability, our study will also investigate microbiota-related genes, host genes related to gut microbiome composition, and the genes involved with the gut-microbiota cross-talk. In conclusion, we hope to collect data to help understand if manipulation of the gut microbiome can improve the training response of individuals with a low gene predictor score for $\dot{V}O_{2max}$ trainability.

RESEARCH PLAN

Improving High Intensity Interval Training Response (IMPROVE-HIIT)

Overview

Improve HIIT will examine the association between the gene predictor score for $\dot{V}O_{2max}$ trainability the gut microbiome; and to investigate whether altering the gut microbiome via diet and training influences the $\dot{V}O_{2max}$ training response to HIIT.

Design

Improve HIIT is an 8-week randomised trial with two groups allocated to either: (1) HIIT plus placebo; or (2) HIIT plus prebiotic

Study Population

Consenting adults aged over 18 years.

Power Calculation (sample size justification)

The proposed project will be a pilot study. Considering financial resources, a sample size of 40 is possible. When using G*Power (download.cnet.com) ([52]), a sample size of 39 will achieve a medium effect size of 0.22 (using 6 predictors). This participant number is similar to a previous study examining if gut taxa is related to $\dot{V}O_{2max}$ levels [12]. A linear multiple regression model was used to include covariates that may contribute to the overall outcome (e.g. 6 predictors may include BMI, age, gender, initial $\dot{V}O_{2max}$, initial gut microbiome and cholesterol levels). Below are results of the power calculation:

F tests - Multiple Regression: Special (R^2 increase)

Analysis: A priori: Compute required sample size

Input:	Effect size f^2	= 0.22
	α err prob	= 0.05
	Power (1- β err prob)	= 0.8
	Numerator df	= 1
	Number of predictors	= 6
Output:	Noncentrality parameter λ	= 8.58
	Critical F	= 4.149097
	Denominator df	= 32
	Total sample size	= 39
	Actual power	= 0.8106

Recruitment

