All non-coded records will be stored in a locked filing cabinet with restricted access for a minimum of five years in a private office of [name]. Any information obtained for the purpose of this research project that can identify a participant will be treated as confidential and securely stored. All computer records will be stored on an access-restricted and file-encrypted network (UQ's Research Data Management System). Only the Principal Investigator and Co-Investigators will have access to project's documents. It will be disclosed only with permission, or as permitted by law.

Data Collection

Primary outcomes

A panel of genetic variants will be identified from a saliva sample collected at baseline via an Oragene collection kit. Saliva samples will be sent to the Translational Research Institute (TRI) for DNA extraction and GWAS analysis. The GWAS will target predictor genes identified from our PREDICT HIIT study.

GWAS analysis

a) DNA extraction from saliva

DNA will be extracted from the stabilised saliva samples using the QIASymphony (Qiagen) DNA MIDI Kit (Cat.no. 937255). The yield and purity will be measured using the Trinean DropSense-96 as per the manufacturer's instructions.

b) Genotyping

100ng of DNA will be genotyped on Illumina Infinium HumanCoreExome24v1.1 arrays as per manufacturer's instructions. The arrays will be scanned on an Illumina iScan system and the raw fluorescence intensity data normalized and clustered for each sample using Illumina Genome Studio (v. 2011.1). Genotypes will be called using the standard Illumina HumanCoreExome24v1.1 cluster file.

c) GWAS

The program PLINK will be used to convert the .ped and .map files into .fam, .bim and .bed files. To this data, clinical files (co-variables and phenotypes) will be added. Data is filtered via the following steps: 1) sample level (call rate, heterozygosity, relatedness, ancestry), 2) SNP level (call rate, minor allele frequency, HWE). Two new types of data will be created: 1) principal components for capturing population-substructure, and 2) genotypes of untyped SNPs (using sanger imputation server for the imputations with HRC r1.1 as reference). Logistic regression will be performed with 'N' PCA components (N is unknown until we do the experiments). SNP coordinates are from the Genome Reference Consortium GRCh37 (hg19) build. A Manhattan plot will be created to visualise the significant genetic markers and raw density plot will be examined manually.

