Investigating whether altering the gut microbiome via diet and training influences the $\dot{V}O_{2max}$ training response to HIIT

The change in $\dot{V}O_{2max}$ of each participant will be calculated. Low responders will be classified by a $\dot{V}O_{2peak}$ change of <100ml of O_2 /min, and high responders by a $\dot{V}O_{2peak}$ change of > 700ml in O_2 /min (following the intervention period).

To compare the mean change in OTUs, alpha diversity, fibre intake and butyrate production to $\dot{V}O_{2max}$ training response, a one-way analysis of co-variance (ANCOVA) will be calculated (with age, sex, baseline $\dot{V}O_{2max}$ as covariates).

A multiple regression analysis will be used to evaluate the role of possible predictors for change in $\dot{V}O_{2max}$. Predictors will be screened using a Spearman correlation matrix to find the top four significant variables to include in the multiple regression analysis (e.g. gene predictor score, sex, age, gender, BMI, fibre intake, OTUs, butyrate production, alpha diversity).

The above approach will also be used to compare changes in other biomarkers (e.g. blood tests, body fat percentage etc).

All statistical tests will be performed at a 5% significance level.

1. Montero, D. and C. Lundby, *Refuting the myth of non-response to exercise training: 'non-responders' do respond to higher dose of training*. JAP, 2017.
2. Mann, T., R. Lamberts, and M. Lambert, *High responders and low responders: factors associated with individual variation in response to standardized training*. Sports Med, 2014. **44**(8): p. 1113-1124.
3. Bouchard, C., et al., *Personalized preventive medicine: genetics and the response to regular exercise in preventive interventions*. Prog Cardiovasc Dis, 2015. **57**(4): p. 337-46.
4. Rankinen, T. and C. Bouchard, *Genetic predictors of exercise training response*. Current Cardiovascular Risk Reports, 2011. **5**(4): p. 368-372.
6. Williams, C., et al., *Genes to predict VO2max trainability: a systematic review*. BMC Genomics, 2017. **18**(Suppl 8:831).
7. Astorino, T. and M. Schubert, *Individual responses to completion of short-term and chronic interval training: a retrospective study*. PLoS One, 2014. **9**(5): p. e97638.

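### The GWAS step fixes logistic regression and a plot of significant markers without naming a binary outcome, while the training response is a continuous change analysed by multiple regression

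*Protocol*

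**What the plan says.** All references are to the protocol.

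- **Model.** Data Collection, GWAS analysis, part c: "Logistic regression will be performed with 'N' PCA components (N is unknown until we do the experiments".
- **Outcome.** The same part says that "clinical files (co-variables and phenotypes) will be added". It does not say which phenotype is the dependent variable.
- **Output.** "A Manhattan plot will be created to visualise the significant genetic markers". Imputation of untyped SNPs is also planned.
- **Scope.** The opening of Data Collection, under Primary outcomes, says: "The GWAS will target predictor genes identified from our PREDICT HIIT study".
- **Training response.** The Statistical Analysis section calculates each participant's change in VO2max and uses multiple regression to look for its predictors. The gene predictor score is among the candidates. Its variants come from PREDICT HIIT, not from this trial's scan.
- **Response classes.** Low responders have a "change of <100ml of O_2 /min, and high responders by a" change above 700 mL/min. No class is given to changes from 100 to 700 mL/min, and the classes are not tied to the GWAS.
- **Effect per variant.** The Background describes trainability as polygenic, "with each genetic variant likely to be contributing a small percentage (typically less than 1%) to the overall change in" VO2max.
- **Significance level.** Statistical Analysis sets 5% for all tests.
- **Sample size.** "Considering financial resources, a sample size of 40 is possible"; the only power calculation is for a linear multiple regression.

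**The concern.** Logistic regression needs a categorical outcome, and this section supplies none. The trait that the rest of the plan ties to genotype is chiefly the VO2peak training response, which is measured and analysed as a continuous quantity. An analyst who follows the GWAS text has to invent a binary outcome. The nearest one in the document is the low/high responder split, which leaves out everyone in between.

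Two things are at stake. Used as written, that split would discard most of the 40 participants. Separately, a plot of significant markers under a blanket 5% level invites reporting of chance findings. Genetic variants are listed under Primary outcomes and results are meant for publication and for a summary to participants, so such markers would be seen.

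**Working it through.** **1. The plan's own figure.** Power section inputs: f² = 0.22, α = 0.05, numerator df = 1, 6 predictors. With N = 39, λ = 0.22 × 39 = 8.58, denominator df = 39 − 6 − 1 = 32, and critical F = 4.1491. Power from the noncentral F is 0.8106; N = 38 gives 0.7998. The stated 39 reproduces. It covers one term in a linear regression with f² = 0.22, that is, a partial R² of 0.22/1.22 = 0.18. It does not cover single variants at or below 1%.

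**2. How many people the response classes leave out.** Assumption, not in the protocol: the change is normal with mean μ of 200 to 400 and SD σ of 150 to 250 mL/min. Then low = 40 × Φ((100 − μ)/σ), high = 40 × [1 − Φ((700 − μ)/σ)], and the rest are unclassified.

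| μ, σ (mL/min) | Low | High | Unclassified |
|---|---|---|---|
| 200, 250 | 13.8 | 0.9 | 25.3 |
| 250, 200 | 9.1 | 0.5 | 30.4 |
| 300, 200 | 6.3 | 0.9 | 32.7 |
| 400, 150 | 0.9 | 0.9 | 38.2 |
| 400, 250 | 4.6 | 4.6 | 30.8 |

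Over the whole grid, 25 to 38 people are unclassified and about 2 to 15 remain. The smaller class never exceeds 4.6 people. A logistic model with an intercept, a variant and several components cannot be estimated stably from that.

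**3. Cost of a binary outcome that keeps everyone.** A simulation with n = 40, 1,000 replicates, assumed minor allele frequency 0.3 and 2 to 10 components compared logistic regression on a median split with linear regression on the continuous change, at α = 0.05.

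| Variance explained by the variant | Logistic power | Linear power |
|---|---|---|
| 10% | 0.31–0.34 | 0.39–0.50 |
| 20% | 0.52–0.62 | 0.73–0.84 |

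Here the logistic model is workable but loses power.

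**4. Per-variant testing under the better model.** Take linear regression, n = 40, R² = 0.01 (the top of the protocol's typical range), the variant plus 4 covariates. Then f² = 0.01/0.99, λ = 40 × 0.0101 = 0.404 and df = 40 − 5 − 1 = 34.

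| α | Power |
|---|---|
| 0.05 | 0.095 |
| 0.05/97 = 0.000515 | 0.0019 |
| 5 × 10⁻⁸ | 4 × 10⁻⁷ |

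The divisor 97 is an assumed number of tests, taken from the count of genes in the Background. The level 5 × 10⁻⁸ appears in the protocol only for a cited study. With 5 components, 80% power for R² = 0.01 at α = 0.05 needs N = 779.

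**5. What a 5% hit would mean.** At df = 34 the critical F is 4.13, so a variant reaches p < 0.05 only if its observed partial R² is at least 4.13/(4.13 + 34) = 0.108. Any flagged variant would therefore look at least ten times stronger than 1%. A true 1% variant is flagged only 0.095/0.05 = 1.9 times as often as a null one. In a genome-wide plot, 0.05 × 100,000 = 5,000 of every 100,000 null variants would be flagged.

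**The case against.** The strongest defence is that no mismatch is proven. The GWAS section names no dependent variable, and one secondary hypothesis is about lower versus higher responders, a two-way contrast that logistic regression suits. This stands in part: the defect is an unnamed phenotype at odds with the rest of the plan, not a demonstrated wrong model. But that hypothesis concerns the gene predictor score rather than single variants, and the response classes in Statistical Analysis do not assign everyone. Details may also sit in a statistical analysis plan, but the choice of logistic regression is fixed here.

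Three stronger readings are tempting, and the documents do not support them.

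- *The whole genetic analysis is unusable.* The score takes its variants from PREDICT HIIT, and Statistical Analysis lists it as a candidate in a multiple regression. It does not depend on this scan, and neither does the comparison of prebiotic with placebo.
- *Leaving the number of components open lets the adjustment be chosen after the results.* The components come from genotypes and capture population structure. Setting their number once the genotypes are in is ordinary practice.
- *The low power shows that logistic regression is the fault.* The figures in step 4 are for linear regression. They reflect 40 people and small effects, and would be poor under any model.

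It is also fair to say that the counts in step 2 rest on assumed means and SDs and on using the responder cut-offs as the GWAS outcome, a link that the protocol does not make.

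**Conclusion.** The point holds in a limited form. The GWAS section prescribes logistic regression and a display of significant markers without a binary phenotype, and this conflicts with the continuous response analysed elsewhere. If the only response classes in the document were used, about 25 to 38 of 40 people would drop out (assumed mean 200 to 400, SD 150 to 250 mL/min) and the model would be unstable.

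Separately, and whichever model is used, per-variant significance at 5% would be mostly noise in a genome-wide plot and nearly uninformative even for a targeted list. Power for a 1% variant is about 9% at 0.05 and 0.2% at 0.05/97. These power figures assume R² = 0.01 and four covariates; varying the number of components from 2 to 10 hardly changes them.

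The section should be corrected, but the trial's main comparison and the gene predictor score are not put in doubt.

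**What to change.** In Data Collection, GWAS analysis, part c:

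1. Name the phenotype as the continuous change in VO2peak and state its unit. The fitness test section reports mL/kg/min, while the responder cut-offs are in mL/min.
2. Replace logistic with linear regression on all participants. The number of ancestry components can still be set from the genotype data.
3. Restrict per-variant output to the PREDICT HIIT variants that the section says it targets. Report estimates with intervals, label them descriptive, and make no significance claims. Remove the plot of significant markers.
4. State that the gene predictor score, kept continuous in the multiple regression already described in Statistical Analysis, is the inferential genetic analysis.

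The cost is protocol wording and somewhat less analysis. The downside is that there will be no genome-wide plot of significant markers to show. No change to sample size, data collection or the score is needed.

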The following table outlines the information to be collected.

Measure	Pre	Post
Cardiorespiratory Fitness		
VO _{2peak}	X	X
Resting blood pressure	X	X
Resting heart rate	X	X
Maximum heart rate	X	X
Gene Predictor Score		
Total number of variants that contribute to high or low response to training		
Diet History		
Food frequency questionnaire	X	X
24-hour diet recall	X	X
Gut Microbiota		
Diversity	X	X
Short chain fatty acid	X	X
Body Composition		
Weight	X	X

Body mass index	X	X
Waist circumference	X	X
Body fat percentage	X	X
Blood chemistry		
Total Cholesterol	X	X
HDL	X	X
LDL	X	X
Triglycerides	X	X
Glucose	X	X
DNA	X	
Family and Personal Medical History		
Family History of Cardiovascular Disease	X	
History of Illness or Injury	X	
Smoking status	X	
Medications	X	
Exercise habits	X	
CESD-R score	X	X

Statistical Analysis

Determining the association between the gene predictor score and the gut microbiome

Following on from the GWAS, a genetic predisposition score for each participant will be calculated to test for the cumulative effect of multiple alleles on $\dot{V}O_{2peak}$ training response and cardiovascular disease risk factors. Using the genetic variants identified from our PREDICT HIIT study (results yet to be published) and taking the approach used in Thomaes et al. (2011), '0' will be given for a homozygote for alleles associated with a low response to training, '1' for heterozygote for an allele associated with high response, and '2' for homozygotes of an allele associated with high response to training. The $\dot{V}O_{2max}$ scores and other covariates will be collated for each participant. Microba will provide gut bioinformatics for each participant (pre and post intervention). The butyrate production per participant will also be calculated as described above (pre and post intervention). This information (including average fibre intake per participant) will be analysed using SPSS statistical software (IBM SPSS Statistics).

Data will be tested for normality using a Shapiro-Wilk test. Where normality is not found, the Kruskal-Wallis test will be used for comparing between data sets.

To compare the mean OTUs (and other bioinformatics provided by 'Microba'), fibre intake and butyrate production for predicted low and high responders (e.g. gene predictor score), a one-way analysis of co-variance (ANCOVA) will be calculated (with age and sex as covariates).

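### The normality rule sends skewed outcomes to Kruskal-Wallis, which drops the planned age and sex adjustment from comparisons of groups that were not randomised

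*Protocol*

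**What the plan says.** Under Statistical Analysis, in the subsection on the gene predictor score and the gut microbiome, the Protocol states: "Data will be tested for normality using a Shapiro-Wilk test". It continues: "Where normality is not found, the Kruskal-Wallis test will be used for comparing between data sets". The following sentence plans a one-way ANCOVA, "with age and sex as covariates", comparing OTUs, other bioinformatics, fibre intake and butyrate between predicted low and high responders.

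The next subsection, on the VO2max training response, plans a further ANCOVA: "To compare the mean change in OTUs, alpha diversity, fibre intake and butyrate production" against training response, "with age, sex, baseline $\dot{V}O_{2max}$ as covariates". It then adds: "The above approach will also be used to compare changes in other biomarkers", with blood tests and body fat percentage as examples.

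No transformation, rank-based ANCOVA or check of model residuals is named anywhere in the section. The normality rule appears once, under the gene-score heading. Neither ANCOVA lists the baseline value of a gut or short-chain fatty acid (SCFA) outcome as a covariate.

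**The concern.** ANCOVA needs approximately normal residuals, not normal raw data, so the pre-test examines the wrong quantity. When it fails, the replacement test cannot carry the covariates specified one sentence later. Whether an outcome is adjusted would then depend on its marginal distribution and not on the question asked.

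This matters most because the gene-score comparison is observational. Predicted low and high responders are not randomised groups. Nor are observed response classes, if these define the comparison in the training-response subsection. Age and sex are in the model to protect such comparisons. Outcomes sent to Kruskal-Wallis would have no such protection, and no adjusted estimate or interval would come from that test.

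**Working it through.** **1. The plan's own figure.** Power Calculation gives f² = 0.22, α = 0.05, 1 numerator df and 6 predictors. With N = 39: denominator df = 39 − 6 − 1 = 32; λ = 0.22 × 39 = 8.58; critical F(1, 32) = 4.149097; power from the noncentral F = 0.8106. All agree with the Protocol. The sample size therefore rests on a covariate-adjusted model.

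**2. What the switch removes.** Kruskal-Wallis uses only the ranks of the outcome and the group labels, so its p-value is the same whatever the participants' ages and sexes. Age and sex are lost in the gene-score comparison. If the rule also governs the training-response subsection, baseline VO2max is lost there too.

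**3. How often it would act.** The Protocol gives no skewness, so log-normal outcomes with a range of log-scale SDs are assumed, n = 40.
- Levels: Shapiro-Wilk rejects in 91-99% of data sets at log-scale SD 0.5 and in 100% at 1.0.
- Changes between two log-normal values (assumed pre-post correlation 0.5-0.7): about 14-17% at SD 0.3, 40-44% at 0.5, 77-80% at 0.8 and 92% at 1.0.

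Skewed levels would almost always be switched. Changes would be switched in some cases and not in others.

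**4. Confounding.** Assumptions: 20 per group, log-normal outcome, no true group effect, sex split 70/30 (14 against 6). With residual SD 1 and half the sample of each sex, the sex effect is β = 2√(R²/(1 − R²)). The spurious group difference is β × (0.7 − 0.3).

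| Variance explained by sex | β | Spurious difference (residual SD) | Kruskal-Wallis rejects | Log or rank ANCOVA rejects |
|---|---|---|---|---|
| 10% | 0.67 | 0.27 | 11% | 5-6% |
| 20% | 1.00 | 0.40 | 17% | 5-6% |
| 30% | 1.31 | 0.52 | 26% | 5-6% |

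A repeat gave 11/18/24% for Kruskal-Wallis. At 60/40 the spurious difference halves and Kruskal-Wallis rejects in about 5-7%. At an exact 50/50 split it is conservative, at 2-4%.

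**5. Power.** Assumptions: two groups of 20, three balanced covariates, adjusted effect d = 2√0.22 = 0.94 residual SD, log-scale SD 1.0, 6,000 runs per cell.

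| Covariate R² | Protocol's rule (ends in Kruskal-Wallis) | Log-scale ANCOVA | Rank ANCOVA | Raw-scale ANCOVA |
|---|---|---|---|---|
| 0 | 0.81 | 0.80 | 0.78 | 0.59 |
| 0.1 | 0.76 | 0.79 | 0.77 | 0.56 |
| 0.2 | 0.71 | 0.79 | 0.76 | 0.51 |
| 0.3 | 0.65 | 0.79 | 0.76 | 0.47 |
| 0.5 | 0.51 | 0.79 | 0.74 | 0.36 |

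The loss against log-scale ANCOVA is about 0, 3, 8, 14 and 28 points. A second set of runs gave 3-4 points at R² of 0 to 0.1, then 10, 16 and 37 at 0.2, 0.3 and 0.5. As a check, the unadjusted effect is d√(1 − R²). At R² = 0.5 that is 0.94 × 0.71 = 0.66, and a normal approximation with rank efficiency 0.955 gives power 0.54.

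**6. Type I error with balanced covariates.** The two-stage rule rejects in 4.7% and 5.2% of null trials (log-scale SD 1.0 and 0.5).

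**The case against.** Several stronger readings are tempting, and the Protocol does not support them.

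- A reader might infer that gut and SCFA outcomes lose adjustment for their own baseline. None was planned. The only baseline covariate is VO2max, and only in the training-response ANCOVA.
- A reader might infer a large loss of power. That depends on how much of a gut outcome age, sex and baseline VO2max explain, which the Protocol does not say. At R² of 0.1 or less the loss is at most about 4 points.
- The loss is measured against a transformed model that the Protocol does not plan. Against raw-scale ANCOVA, Kruskal-Wallis is ahead at every R² shown for log-scale SD 1.0. At log-scale SD 0.5 it leads up to R² = 0.1 (0.77 against 0.73) and trails at 0.5 (0.51 against 0.63).
- A reader might infer that the pre-test itself inflates type I error. With balanced covariates it does not. The inflation in step 4 comes from imbalance that is left unadjusted.
- Placed under the gene-score heading, the rule reaches the training-response ANCOVA only by a reasonable reading. The multiple regression for change in VO2max has no stated Kruskal-Wallis replacement.

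All of these limits stand. It can also be said that the wording does not expressly say that Kruskal-Wallis replaces the ANCOVA, and that this is a pilot. But the rule comes immediately before the ANCOVA it would affect, and no other use for it is given. It is a stated rule, not a detail left to a later plan.

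**Conclusion.** The concern holds in a limited form. The rule removes age and sex adjustment from outcomes that fail a normality test on the data, in a comparison of groups that were not randomised, and so makes adjustment differ between outcomes. The main consequence is exposure to confounding: false rejection of about 11-26% under an assumed 70/30 sex split with sex explaining 10-30% of log-scale variance, and close to nominal at 60/40. The actual imbalance, the sizes of the gene-score groups and the strength of the sex effect are not in the Protocol.

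The power cost is secondary and conditional: 0-4 points at covariate R² of 0.1 or less, 8-10 at 0.2, 14-16 at 0.3 and 28-37 at 0.5. The simulations assume log-normal outcomes and 20 per group, and the power runs also assume three independent, balanced covariates. They do not reproduce the exact planned comparisons. The change is worth making, but this is not a fault in the randomised comparison or in the VO2max regression.

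**What to change.** Replace the switch with one pre-specified covariate-adjusted model per outcome. Deleting it alone is not enough, because raw-scale ANCOVA does poorly on strongly skewed data.

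- Log-transform SCFA values and log-ratio transform abundances at each visit. For change outcomes, take the difference of the transformed values, since a raw change can be negative and cannot be logged.
- Judge the fit on model residuals. Where these remain poor, use a rank-based ANCOVA or a permutation p-value with the same covariates.
- State whether the rule applies to the training-response subsection and to the other biomarkers.

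The cost is wording only: no extra data or participants. Effects for log-transformed outcomes would be reported as ratios.
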